Official Grant Title: Virtual Human Technology for Patients with Chronic Pain

Working Title: Virtual Human–Delivered Interviews for Patients with Chronic Pain: Feasibility, Acceptability, and a Pilot Randomized Trial of Standard Medical, Psychosocial, and Educational Interviews

NCT #: 04349033

Date: October 15, 2021

Statistical Analysis Plan

To test our aim (whether interviews affected pain-related outcomes about one month later), we will conduct intent-to-treat (ITT) analyses using data from all patients, accommodating missing values on outcomes using maximum likelihood parameter estimation. Two-way repeated-measures ANOVAs with one between-subjects factor (experimental condition) and one within-subject factor (time) will be tested using linear mixed effects models (using the MIXED procedure in SAS 9.4; Cary, NC). Analyses will focus on time by group interactions (indicating group differences in change from baseline) for two specific comparisons: 1) Psychosocial vs. Standard; and 2) Educational vs. Standard. We will also inspect changes from baseline within each of the three experimental conditions separately using post-hoc contrasts. We will include VH voice (human vs. computer) as a covariate in all models and include age and education as covariates in sensitivity analyses.

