Chronic pain is accompanied by a host of emotional, behavioral, and cognitive psychosocial consequences. At the same time, psychosocial factors contribute to chronic pain, including fear of movement and catastrophizing, maladaptive emotional and cognitive processes, and adverse life experiences. Treatment guidelines stress the importance of psychosocial aspects in pain management. Unfortunately, both patients and medical providers find it difficult to discuss psychosocial problems. The goal of this project is to remedy this critical problem by developing and pilot testing novel therapeutic interviews delivered by next-generation Virtual Humans (VHs) to help patients engage in discussions about pain-related psychosocial factors. In this IRB application, we will develop VH-assisted therapeutic psychosocial interviews specifically for chronic pain. Three Virtual Human interview scripts will be developed: One that facilitates participant disclosure of psychological distress, coping, medication usage, and stressful live events; one that mirrors this condition but includes explanations of how the mind contributes to chronic pain, and a control condition that asks about participants' medical history, medications, and chronic pain background. Adult patients who experience chronic musculoskeletal pain, are fluent in English, have no visual and cognitive impairment that would interfere with participation, have an average pain score of 4 or higher during the past week on a 0 to 10-point scale, and are receiving treatment for their chronic pain will be recruited through flyers from the Keck Medical School and invited to participate in a session with a Virtual Human at USC's Institute for Creative Technologies (ICT). Each patient who agrees to participate will come to ICT and will be assigned to one of the three VH conditions. The session at ICT consists of written informed consent followed by online questionnaires (e.g., demographics, mental and physical health, stressful live events, pain medication usage, coping), followed by the VH session, followed by post-session online questionnaires (e.g., satisfaction with the VH session), and then a brief structured interview with a research assistant about patients' experience with the VH. Patients will also be invited to participate in a brief online survey one month after the session with the VH at ICT. Patients will be compensated \$70 via Amazon gift card for the 1 1/2 to 2 hour session at ICT and an additional \$10 via Amazon gift card, if they agree to complete the online survey about one month after the study visit at ICT. Based on participant feedback (qualitative and quantitative), the Virtual Human interviews will be refined as necessary to improve the sessions.

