
Describe the inclusion criteria for enrollment.

Adult patients who experience chronic musculoskeletal pain (e.g., pain in the neck, back, arms, and legs) will be recruited via flyers from the Keck Medical School (e.g., the Keck Pain Center). Patients are eligible to participate if they (1) are 21 years or older, (2) experience chronic musculoskeletal pain (i.e., pain for at least three months), (3) are fluent in English, (4) have no visual/cognitive impairment that would interfere with participation in the study, (5) receive treatment for their chronic pain, and (6) report an average pain severity during the past week of 4

or greater on a 0 to 10 point scale, and (7) are willing to participate in a 1 1/2 to 2 hour session at USC's Institute for Creative Technologies.

Describe the exclusion criteria for enrollment.

1) younger than 21 years, (2) no chronic musculoskeletal pain, (3) not fluent in English, (4) visual/cognitive impairment that would interfere with participation in the study, (5) not in treatment for chronic pain, and (6) average pain severity during the past week lower than 4 on a 0 to 10 point scale, (7) not willing to participate in a 1 1/2 to 2 hour session at USC's Institute for Creative Technologies.

If there are any age, ethnic, language, or gender-based exclusion criteria, please provide justification.

Patients must be fluent in English and adults as the Virtual Human interview scripts are developed in the English language and for adults.

Research Objectives and Background

Describe the specific objectives or aims of the study and hypotheses or research questions.

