Our team at the University of Southern California's Institute for Creative Technologies consists of world leaders in the development of Virtual Human technology for health research. ICT has successfully developed Virtual Human prototypes and conducted many research studies at USC that relate to the proposed project with minimal risk to participants.

Methods and Procedures - Prospective Studies

Describe in detail the design and methodology of the study. Provide a detailed description of the planned data collection, specific outcomes, and criteria for evaluation and endpoint definition. If applicable, include information on stratification or randomization plans. Include the frequency and duration of each activity and the total length of subject participation.

If patients volunteer to participate in this study, they will schedule an individual 1.5 to 2-hour session at USC's ICT. At ICT, they will first read and sign a study consent form before entering the study. They will also get a copy of the consent form to keep. The research team will answer any questions they may have about the study before patients decide to participate. Once patients have agreed to participate and signed the consent form, they will be asked to complete four parts of this study. These are:

- 1) an online general health and well-being survey (approx. 15-20 minutes),
- 2) an interview with a Virtual Human about their life with chronic pain (approx. 45-60 minutes)
- 3) an online questionnaire after their Virtual Human interview (approx. 15 minutes), and
- 4) an interview with research staff about their experience with the Virtual Human (approx. 15 minutes).

Patients' overall time commitment for this study is expected to be between 1 and 2 hours and they will be compensated with \$70 via Amazon gift card for their participation in this session at ICT.

Patients will also be invited to complete a brief (approx. 15 minutes) online questionnaire

(e.g., about their continued satisfaction with the Virtual Human session) about one month after the session at ICT that they can complete from their home computer. If patients agree to complete the survey, they will receive an additional \$10 via Amazon gift card.

Gift cards will be emailed to patients about 4 weeks after their participation in the ICT session and the one-month post ICT session online survey.

During their visit at ICT:

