- 1) We will ask patients to complete different questionnaires pertaining to their demographics and medical background, their emotions, chronic pain management and medication usage, and stressful events. These questionnaires will be completed in an online survey before and after the interview with a Virtual Human and in the brief online survey about a month after the visit at ICT for the study.
- 2) Patients will also be asked to interact with a Virtual Human interviewer. This study has three different types of interviews, and patients will be assigned to one of them. In the course of this interaction, they will be asked to answer personal questions, such as about their emotions, stressful life experiences, how they cope with chronic pain, and their medical treatment and pain medication usage for chronic pain. The Virtual Human interview will be audio-recorded for analysis purposes.
- 3) At the end of the ICT study visit, we will ask patients to tell us about their experiences with the Virtual Human in a structured interview with our research staff. The goal of this interview is to learn how they felt about their interaction with the Virtual Human and if we can improve the interviews. This interview with research staff will also be audio-recorded for analysis purposes.

If patients do not want to be audio-recorded, they cannot participate in this research study.

Describe the statistical considerations for the study, how the sample size was determined, and how the results will be analyzed, if applicable.

Pilot studies typically consist of relatively small sample sizes and our proposed study sample consists of 35 to 50 patients. Given that this study will iteratively refine the Virtual Human interview scripts depending upon participant feedback, we will recruit up to 50 participants, if the Virtual Human scripts more need refinement. Patient feedback will be in the form of qualitative (e.g., a brief structured interview with a research assistant at ICT) and quantitative (e.g., standard questionnaires) data. These data will inform us whether the Virtual Human interview scripts function as intended, need improvement, and whether participants enjoyed the interaction with the Virtual Human. The majority of patients will be assigned to the two psychosocial Virtual Human conditions and fewer to the control condition.

Deception

Describe why the research cannot be carried out without deception.

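### Does the SAP need to name its pain outcomes before the one-month comparison can be analysed?

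*SAP*

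**What the plan says.** The SAP is a single paragraph. Its aim is to learn "whether interviews affected pain-related outcomes about one month later". It specifies repeated-measures ANOVAs, fitted as linear mixed models by maximum likelihood to data from all patients. Then: "Analyses will focus on time by group interactions (indicating group differences in change from baseline) for two specific comparisons", namely Psychosocial against Standard and Educational against Standard. Voice type is a covariate throughout, with age and education added in sensitivity analyses. No instrument, score, primary outcome or alpha level is given.

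The protocol form, under Methods and Procedures - Prospective Studies, carries the prompt "Provide a detailed description of the planned data collection, specific outcomes, and criteria for evaluation and endpoint definition". The answer works by topic. Patients complete "questionnaires pertaining to their demographics and medical background, their emotions, chronic pain management and medication usage, and stressful events". As to timing, these are "completed in an online survey before and after the interview with a Virtual Human and in the brief online survey about a month after" (that is, following the session). An earlier paragraph of the same section describes the one-month questionnaire with a single example, "about their continued satisfaction with the Virtual Human session) about one month after the session at ICT".

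The one pain measure with a stated scale is an entry criterion. Under inclusion criteria, patients must "report an average pain severity during the past week of 4" or more, and the study summary says the same: "have an average pain score of 4 or higher during the past week on a 0 to 10-point scale".

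**The concern.** A plan that says it will test an aim would normally say on which variable. Here the form asks for endpoint definitions and gets survey topics in reply. The only example for the one-month survey, satisfaction with the session, cannot have a pre-session value, so it cannot enter a change-from-baseline contrast. At least three things could count as pain-related: past-week severity, pain management and medication use. Each of the last two could yield more than one score.

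Two matters would be at stake. An analyst could favour whichever score looked best once the one-month data were in. And each added outcome brings two more contrasts, so the chance of an isolated false positive rises.

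**Working it through.** **1. What the SAP's own model admits.** A score must be measured before the session and again at one month, and it must be pain-related. Set against the protocol:

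| Candidate | Placed in pre-session and one-month surveys? | Can enter the contrast? |
|---|---|---|
| Satisfaction with the session | No baseline possible | No |
| Demographics, medical background, stressful events | Yes, as topics | Not pain outcomes in themselves |
| Emotions | Yes, as a topic | Only if a score is pain-specific |
| Pain management | Yes, as a topic | Yes |
| Medication use | Yes, as a topic | Yes |
| Past-week severity, 0–10 | Not stated; entry criterion only | Only if asked in both surveys |

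The field is limited by what was collected at both times. With plural outcomes and plural ANOVAs, following the SAP means running one model for each qualifying score, not choosing one.

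**2. Multiplicity, for scale.** The documents state no alpha, so 0.05 is assumed. With k outcomes and two contrasts each, if the tests were independent, the chance of at least one false positive is 1 − 0.95^(2k):

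- k = 1: 1 − 0.95² = 0.0975
- k = 2: 1 − 0.95⁴ = 0.1855
- k = 3: 1 − 0.95⁶ = 0.2649

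The tests are not independent: the two contrasts share the Standard arm, and pain scores move together. The simulation assumed normal changes, complete data, correlations of 0.3 to 0.7 between outcome changes, and splits of 20/20/10, 17/17/16, 14/14/7 and 12/12/11 (Standard last). It gives 8–9% for one outcome, 14–17% for two and 18–24% for three.

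**3. Would two analysts disagree?** If each analyst tested only one outcome, and a different one, the same simulation has them disagreeing on whether either interview differs from Standard in 11–16% of trials with no effect. With a true shift of 0.5 change-SD on every outcome, they disagree in 22–41%. These figures need a yardstick. With one agreed outcome and that same shift, at least one contrast is significant in about p = 27–42% of trials. Two separate trials using that same outcome would then disagree with probability 2p(1 − p):

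- p = 0.27: 2 × 0.27 × 0.73 = 0.39
- p = 0.42: 2 × 0.42 × 0.58 = 0.49

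With no effect, p runs from 0.083 to 0.089:

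- p = 0.083: 2 × 0.083 × 0.917 = 0.15
- p = 0.089: 2 × 0.089 × 0.911 = 0.16

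Much of the disagreement therefore reflects low power. A direct two-sample calculation agrees: a single contrast at 0.5 SD has power between 0.189 (35 patients, 7 in Standard) and 0.303 (50 patients, equal arms).

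**4. What naming an outcome would alter.** The models, covariates, contrasts, estimates and intervals would be the same. One outcome would be called primary and the rest exploratory. Choosing past-week severity because it has a stated scale would be debatable, since neither document places it in either survey. Patients are also selected for scoring 4 or more on it, so within-condition falls from baseline would be exposed to regression to the mean.

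**The case for a change.** The strongest case for acting is that the text check holds without any simulation. The SAP says it tests an aim, calls the study a pilot randomised trial, and does not say which result answers the aim. Pilot status lowers the need for error control but does not supply a definition, a topic is not a score, and a list would cost a few lines. If only the favourable score were published, the reader could not tell from these documents. With three outcomes and no effect, the largest apparent benefit averages 0.30–0.48 change-SD, against 0.13–0.17 with one.

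The factual part stands: no list and no hierarchy appear in either document, and a list would make selective reporting easier to detect. What does not stand is the step from there to a faulty analysis. The largest-benefit figure describes picking one outcome from several, which the SAP does not plan. The number of outcomes is itself an assumption, and it drives every magnitude quoted.

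**Conclusion.** No change to the plan is called for. The missing list is a detail that analysts fill sensibly by fitting the specified model to every pain score available at both times and reporting all of them. No number or rule in the SAP is wrong. The protocol's stated use of the data is to learn whether the scripts work, need improvement and are enjoyed, and the SAP's title puts feasibility and acceptability ahead of the pilot comparison. Nothing in either document makes a decision depend on one significant pain result.

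The residual cost is a family-wise false-positive chance of about 18–24% instead of 8–9%, under an assumed alpha of 0.05, three assumed outcomes and correlations of 0.3 to 0.7. It is tolerable where results are read as pilot estimates. The conclusion rests on that reading and on all qualifying outcomes being reported. It would be different for a confirmatory trial, or if one pain result were presented alone as the answer to the aim.

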The goal of this project is to develop three Virtual Human (VH) interview conditions for patients who experience chronic pain. Two of these VH conditions will focus on participants' disclosure of negative mood, psychological distress, coping with chronic pain, stressful life experiences, pain medication usage, and personality characteristics. The third condition is a control condition that focuses on the medical aspects of patients' chronic pain experience including their pain medication usage. In order to develop the best possible VH interviews, stakeholder feedback by patients is critical. We will, therefore, pilot test the three VH interviews with patients who experience chronic pain to get their qualitative (e.g., structured interview) and quantitative feedback (e.g., questionnaires) about their experience and how the VH interviews could be improved. In order to examine the best features of a Virtual Human coach, we will compare Virtual Humans that deliver the session either with a computer-generated voice or a voice recorded by a real person. Half of the patients in each of the three conditions will hear the computer-generated Virtual Human voice and the other half will hear the voice recorded by a real person. Patient feedback will tell us whether patients might prefer one Virtual Human voice over the other.

Chronic pain is accompanied by a host of emotional, behavioral, and cognitive psychosocial consequences. At the same time, psychosocial factors contribute to chronic pain, including fear of movement and catastrophizing, maladaptive emotional and cognitive processes, and adverse life experiences. Treatment guidelines stress the importance of psychosocial aspects in pain management. Unfortunately, both patients and medical providers find it difficult to discuss psychosocial problems. The goal of this project is to remedy this critical problem by developing and pilot testing novel therapeutic interviews delivered by next-generation

Virtual Humans (VHs) to help patients engage in discussions about pain-related psychosocial factors.

Provide a summary of the background of the study and explain how this research will contribute to existing knowledge. Describe previous work that provides a basis to show that the proposed research can be carried out without undue risk to human subjects. Include relevant citations.

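### If allocation was random, a common-baseline mixed model would usually estimate the two planned contrasts more precisely than the free-baseline interaction test, which is itself valid

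*SAP*

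**What the plan says.** The SAP plans repeated-measures models in SAS MIXED with condition and time as factors. The result of interest is the interaction: "Analyses will focus on time by group interactions (indicating group differences in change from baseline) for two specific comparisons", namely Psychosocial vs. Standard and Educational vs. Standard. It states no constraint on the baseline means and names no covariance structure. Missing outcomes are handled by "accommodating missing values on outcomes using maximum likelihood parameter estimation". On covariates it says: "We will include VH voice (human vs. computer) as a covariate in all models and include age and education as covariates in sensitivity analyses". It does not say whether these enter with time interactions.

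The SAP's working title describes "a Pilot Randomized Trial of Standard Medical, Psychosocial, and Educational Interviews". The protocol speaks only of patients being assigned and describes no random method. Under statistical considerations it gives 35 to 50 patients and says: "The majority of patients will be assigned to the two psychosocial Virtual Human conditions and fewer to the control condition". On voice, the research objectives say: "Half of the patients in each of the three conditions will hear the computer-generated Virtual Human voice". The protocol's opening summary puts the baseline measures first: "online questionnaires (e.g., demographics, mental and physical health, stressful live events, pain medication usage, coping), followed by the VH session". Follow-up at one month is by invitation: "Patients will also be invited to complete a brief (approx. 15 minutes) online questionnaire".

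**The concern.** With two time points, the tested interaction is a difference between arms in mean change. Each arm's observed baseline mean is subtracted in full, chance imbalance included. Under random allocation the arms share one true baseline mean, so estimating three of them usually spends information that the trial has already collected. This matters most with few patients and a small Standard arm that serves both comparisons.

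The covariates raise a related issue. If voice, age and education enter as main effects only, they are constant over time, while the tested term concerns change over time. The age and education sensitivity analysis could then look reassuring mainly because the contrast can hardly respond to it. For voice, a main effect assumes the same difference before and after the session, yet the baseline questionnaires come before any voice is heard.

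**Working it through.** The plan states no variance, power or precision figure, so there is none to reproduce.

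**Inputs.** From the documents: N of 35 to 50, fewer patients in Standard, voice half and half in each arm, pain of at least 4 at entry. Assumed, because the documents are silent: a 2:2:1 split (14/14/7 and 20/20/10), correlation rho, follow-up to baseline SD ratio r, and a fraction d of follow-up missing completely at random. Two time points are taken.

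**Large-sample formula.** Per patient, in units of the baseline variance, with slope b = rho × r:

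- free baseline: r²(1 − rho²)/(1 − d) + (1 − b)²
- common baseline: r²(1 − rho²)/(1 − d)

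The saving is the term (1 − b)² divided by the first line. With complete data it is (1 − rho r)²/(1 + r² − 2 rho r). The split cancels from the ratio.

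Example with rho = 0.5 and r = 1:

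- d = 0: 0.25/(0.75 + 0.25) = 25%
- d = 0.2: 0.25/(0.75/0.8 + 0.25) = 0.25/1.1875 = 21.1%

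**Equal SDs, fall in contrast variance.** The small-sample rows come from 60,000 simulated trials per setting, with the proposed model charged for a voice-by-time term and the free-baseline model charged nothing for voice.

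| rho | 0.4 | 0.5 | 0.6 | 0.7 | 0.8 |
|---|---|---|---|---|---|
| Large sample, complete | 30% | 25% | 20% | 15% | 10% |
| Large sample, 20% missing | 25.5% | 21.1% | 16.7% | 12.4% | 8.2% |
| N=35, 20% missing | 21% | 16% | 12% | 8% | 3-5% |
| N=50, 20% missing | 22% | 18% | 13% | 9% | 3-5% |

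The range 3-5% covers both sample sizes. In standard error, 1 − √0.92 = 4% and 1 − √0.78 = 12%. At rho 0.5 and 20% missing, the 95% interval half-width falls from 0.87 to 0.79 SD (N=50) or from 1.05 to 0.97 SD (N=35).

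**Unequal SDs, large sample, complete data.**

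- r = 0.8: saving of 46.2% at rho 0.4, falling to 36.0% at rho 0.8
- r = 1.25: 16.0% at rho 0.4, 1.9% at rho 0.7, and 0 at rho 0.8, where b = 0.8 × 1.25 = 1
- r = 2, rho 0.8 (b = 1.6): 0.36/1.8 = 20%

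The saving is therefore zero at b = 1 and positive on either side. At b = 1 the extra estimation costs about 1/(N − 6) with complete data: 1/29 = 3.4% at N=35 and 1/44 = 2.3% at N=50. Simulated losses there were 2-4% with complete data, 3-5% with 20% missing and 4-6% with 30% missing.

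**Pain severity.** The entry floor narrows the baseline spread. With a normal baseline (mean 5 to 6, SD 2) truncated at 4, rho 0.4-0.7 and 20% missing, the fall is about 1-15%.

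**Covariates.** In the free-baseline model with complete follow-up, a term that is constant over time drops out of each patient's change, so the interaction estimate is unaffected. In simulation (age effect on follow-up 0.3 SD per SD, education −0.2, slope 0.5), adding age and education as main effects moved the contrast by 0 in all 6,000 complete-data trials. The by-time versions moved it with SD 0.16-0.21 in outcome SD units. With 20% missing completely at random, the shifts had SD 0.03-0.08 and 0.19-0.26.

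**The case against.** The strongest reply is that nothing here is wrong with the plan. The interaction test is a recognised analysis, missing outcomes are handled by likelihood, and a pilot meant mainly to refine interview scripts states no precision target that it could miss. The intervals stay wide either way. All of this stands, and it limits the point to an optional improvement.

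Four further objections also stand.

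- **Every percentage is assumed.** A reader might take 8-22% as a property of this trial. The documents supply none of the inputs that would support that.
- **Allocation.** The constraint needs randomization, which the SAP title states and the protocol does not describe.
- **Time points.** The protocol's visit description has questionnaires before and after the interview and again at about one month, so some outcomes may have three time points. The formula and simulations cover two.
- **Covariates.** A reader might infer that the age and education analysis can show nothing. Entry as main effects only is a reading of the SAP's wording, and the simulations above assume completely random dropout. In a check at N=50 with equal age effects at both times and strong age-related dropout running in opposite directions by arm (an assumed extreme), mean error fell from 0.114 unadjusted to 0.013 with main effects and 0.012 by time. With effects at follow-up only, main effects took it from 0.205 to just 0.164, and by-time terms to −0.005. Main effects can therefore matter when dropout depends on them.

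**Conclusion.** The point holds as an efficiency suggestion. If allocation was random, the common-baseline model is usually more precise for both named contrasts. On the assumptions of a 2:2:1 split, equal SDs, 20% missing completely at random and rho 0.4-0.7, the fall in variance is about 8-22% at N 35-50. It is about 3-5% at rho 0.8, and about 1-15% for truncated pain severity.

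Two stronger readings are not supported. One is that the planned test is biased or invalid: under random allocation both estimators were unbiased in simulation. The other is that the gain disappears whenever follow-up is much more variable than baseline. It disappears only near a slope of 1, which at rho 0.8 needs an SD ratio of just 1.25, and it returns beyond that.

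The covariate point is secondary: exact for complete follow-up if the terms are main effects only, approximate under completely random dropout, and not general.

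**What to change.** Keep MIXED and the same two contrasts, and specify an unstructured covariance. Constrain the baseline mean to be common across arms by fitting time plus group by post-baseline time, with no group effect at baseline. Include the post-session time point for any outcome measured then. Keep the free-baseline test as a secondary analysis. State in the SAP how patients were allocated; if allocation was not random, keep the free-baseline model as primary.

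As a supporting change, add voice-by-time to the models, and age-by-time and education-by-time to the sensitivity analysis. These additions apply whichever baseline model is used. The within-arm post-hoc contrasts can stay as planned.

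The cost is SAP wording and a small change to the MODEL statement, with no new data. Each by-time term takes about one degree of freedom. The downside is a variance increase of about 2-5% near a slope of 1 with 0-20% missing, and up to 6% with 30% missing.

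### Do the post-hoc within-condition contrasts need a stated limit on what they can prove?

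*SAP*

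**What the plan says.** The SAP opens with a causal aim: "To test our aim (whether interviews affected pain-related outcomes about one month later". Its main analysis is a linear mixed model with condition and time. It says: "Analyses will focus on time by group interactions (indicating group differences in change from baseline) for two specific comparisons", and names these as Psychosocial vs Standard and Educational vs Standard. The next sentence is the one at issue: "We will also inspect changes from baseline within each of the three experimental conditions separately using post-hoc contrasts". Nothing further is said about how those contrasts will be read.

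Three features of the Protocol bear on the point:

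- **Entry.** Patients must "report an average pain severity during the past week of 4" or more on a 0 to 10 scale, and must "receive treatment for their chronic pain" (inclusion criteria).
- **Questionnaires.** They are "completed in an online survey before and after the interview with a Virtual Human", and again about a month later (Methods and Procedures).
- **Size and allocation.** In the statistical considerations, "our proposed study sample consists of 35 to 50 patients", and "The majority of patients will be assigned to the two psychosocial Virtual Human conditions and fewer to the control condition". No ratio is given.

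**The concern.** A change from baseline within one condition is not an effect of the interview. It also contains whatever would have happened to these patients anyway. Here such a shared change is plausible, because everyone enters above a pain threshold and everyone is under treatment. If all three conditions shift by the same amount, chance alone can make one within-condition test significant and another not. If Standard is also the smallest arm, its test is the least likely to reach significance, so the pattern leans towards the psychosocial interviews.

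At stake is a claim that an interview worked, resting on a comparison of p-values when the direct comparison shows nothing. The SAP does not expressly rule out that reading.

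**Working it through.** The planned sample size is justified only as usual for a pilot, so the plan has no figure to reproduce. The check has three parts.

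**1. How often does the misleading pattern arise?** The event is that at least one of the two psychosocial-type conditions changes significantly and Standard does not, when the true change is the same in all three. Assumptions: normal change scores, pooled SD with N − 3 degrees of freedom, two-sided 5%, and four splits of 35 or 50 patients. The documents give neither the splits nor the alpha. The common change is in SDs of the change score.

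A hand check with no common change and independent tests gives (1 − 0.95²) × 0.95 = 0.093. With 14/14/7, a common change of 0.5 SD and separate paired t tests, power is 0.41, 0.41 and 0.20, so [1 − 0.59²] × 0.80 = 0.52. Simulation with the pooled SD (200,000 trials per cell) gives:

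| Common change | 12/12/11 | 14/14/7 | 17/17/16 | 20/20/10 |
|---|---|---|---|---|
| 0 | 8.9% | 8.9% | 9.2% | 9.1% |
| 0.15 | 13.6% | 14.6% | 15.9% | 17.4% |
| 0.25 | 21.2% | 23.9% | 25.7% | 30.4% |
| 0.35 | 29.6% | 35.6% | 35.1% | 44.0% |
| 0.5 | 38.3% | 50.1% | 37.7% | 53.9% |
| 1.0 | 10.3% | 27.1% | 2.6% | 12.7% |
| 1.2 | 2.9% | 13.0% | 0.3% | 3.9% |

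At least one of the two planned between-condition contrasts is falsely significant in 8% to 9% of trials, whatever the common change. The pattern is therefore more frequent than that at small to moderate common change. At large common change it recedes, because Standard becomes significant too: it is below the planned contrasts' rate at 1.2 SD for three of the four splits, though not for 14/14/7.

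The more persuasive version, both psychosocial-type conditions significant and Standard not, is rarer: 0.7% to 1.1% at 0.15 SD and 1.8% to 3.6% at 0.25 SD.

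**2. How large a common change do the documents support?** The only source that can be approximated is regression to the mean from the pain threshold of 4. Assume normal pain scores with mean 4.5 to 6 and SD 2. The mean excess of a selected patient is then λ = 0.646 down to 0.288 SDs.

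- *If the screening score is the baseline:* fall = (1 − ρ) × SD × λ. With ρ = 0.5 and mean 4.5 this is 0.5 × 2 × 0.646 = 0.65 points. With ρ = 0.7 and mean 6 it is 0.3 × 2 × 0.288 = 0.17 points. Divided by the SD of change in the selected sample (1.85 and 1.51), these are 0.35 and 0.11 SD.
- *If the baseline is a separate pre-interview questionnaire:* fall = (correlation of screening with baseline − correlation of screening with follow-up) × SD × λ. It is zero if the correlations are equal. If the second is lower by 0.1 to 0.2, the fall is 0.06 to 0.26 points, or about 0.03 to 0.15 SD when baseline and follow-up correlate as screening and follow-up do. A baseline-to-follow-up correlation of 0.8 would lift the top to 0.26/1.23 = 0.21 SD.

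The Protocol has questionnaires completed before the interview, which points to the second case. From the table, 0 to 0.15 SD gives 9% to 17%. The calculation concerns pain severity only, whereas the SAP speaks of pain-related outcomes in general. Being under treatment might add a shared change, but the documents do not quantify one.

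**3. Does the plan use the contrasts in the way feared?** Set side by side, the two SAP sentences form an order. The first ties the analysis to group differences in change and names the two comparisons. The second adds an inspection, labelled post hoc. No sentence draws an interview effect from a within-condition change or compares significance across conditions.

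**The case for a change.** The strongest case for a change is that ranking analyses does not restrict their interpretation. With arms this small the planned contrasts have little power: 80% power needs a difference of (1.96 + 0.84) × √(1/7 + 1/14) = 1.30 SD at 14/14/7, or 1.09 SD at 20/20/10. A non-significant interaction beside a significant psychosocial-arm change is thus a realistic result, and then a written limit would help most. In the simulations, 82% to 92% of trials showing the pattern at 0.25 to 0.5 SD had no significant planned contrast. A remedy would cost a sentence or two.

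The logic stands: differing significance is not a significant difference, and no sentence in either document says so. But this describes a misreading that the SAP does not plan. A sentence confining conclusions to the two interactions would record what the SAP's own focus already implies. Going further and dropping the within-condition tests is a matter of preference. Simple contrasts after a mixed-model interaction are conventional, and in a pilot it helps to know whether each condition improved, worsened or stayed flat. Nor is the risk present at every size of common change: it is slight when that change is near zero and recedes when it is large.

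**Conclusion.** No change is needed. The omission is real, but it is a detail that a competent analyst fills correctly from the text: the two time-by-group contrasts answer the aim, and the within-condition contrasts describe. Followed as written, the plan keeps about an 8% to 9% chance of a false positive on either unadjusted planned contrast, whatever the common change.

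The misleading pattern would appear in about 9% to 17% of trials under the best-supported reading, a separate pre-interview baseline with 0 to 0.15 SD of common change. It harms only if someone reads it against the SAP's stated focus. Rates of 21% to 54% need a common change of 0.25 to 0.5 SD. Regression to the mean reaches part of that range if the screening score serves as baseline (up to 0.35 SD); beyond that, another source is needed, and the documents quantify none. All of these figures rest on assumed splits, SD, correlations and a two-sided 5% level.
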